#### Genetic Analyses:

A one-time 20cc sample will be collected on the first scanning day only from consenting participants for the purpose of extracting DNA to determine whether polymorphisms of physiological systems that are known to influence 5-HT and DA function contribute to binding on the PET/radioligand studies with women who have an eating disorder history. All samples collected will be identified without personal identifiers, but coded, and known only by [name] research team. Genetic samples will be used for eating disorder research, obesity or related disorders. Should a participant withdraw her consent from this genetic testing, the samples will be immediately destroyed. Otherwise, frozen samples will be kept under locked conditions at UCSD in the Eating Disorders Center for Treatment and Research for an indefinite time where they will be submitted for analysis with DNA and lymphocyte extraction. A specific consent for this blood draw will be signed at the time of study consenting if the participant is interested in participating. Blood samples for genetic analysis will be stored in freezers at the Eating Disorders Center for Treatment and Research under supervision of [name]. [name] will be responsible for determining how DNA will be used. The specimens collected and the DNA that they contain may also be used in additional research to be conducted by the University of California personnel collaborating in this research. In addition to [name], subjects DNA may also be studied by other future collaborators that are unknown at this time to learn more about eating disorders, obesity and other related disorders. No more than a total of 105 cc of blood will be drawn for both studies together; this amount is approximately 20-25% of a regular blood donation.

#### Power and Statistical Analysis Plan:

**Aim 1:** In AIM 1 we will use PET and [C]DASB BPND to determine whether there is a continuum of 5-HTT binding associated with diagnosis. We hypothesize that REC AN will show increased and REC BN decreased [C]DASB BPND in midbrain and striatal regions. REC AN-BN will have [C]DASB BPNDs between those of REC AN and REC BN and will probably not differ from CW. These hypotheses will be tested by an unpaired t-test with diagnosis as factor and [C]DASB BPND as dependent variable. We will use Troendle's (1995) method to adjust for multiple comparisons. Our preliminary study found [C]McN5652 BPNDs of 1.169 (CW), 1.316 (AN), 1.027 (BN), and 1.168 (AN-BN) in the dorsal raphe, with a SD of 0.348 or less in each group. [C]McN5652 is an older radioligand and, based on additional pilot data, we expect to see [C]DASB BPNDs that are roughly 2.17-times higher than [C]McN5652 BPNDs in the midbrain, with only a

slight increase in within-group SDs (less than 0.382 for [C]DASB BPND). With 25 subjects per group, a (Welch-Satterthwaite) t-test will have power in excess of 80% to see a difference between the REC AN and CW (based on a mean difference of 0.319 and a within-group SD of 0.382) and REC BN and CW (based on a mean difference of 0.308 and a within-group SD of 0.382) at the 0.05 level (two-sided). We expect the [C]DASB BPND for REC AN-BN to be between that of REC AN and REC BN and (essentially) the same as CW.

**Aim 2A** will compare REC AN, REC AN-BN and REC BN to CW to test the hypothesis that REC AN and REC BN have increased AVS [C]raclopride BPND compared to CW, and to further explore [C]raclopride BPND in REC AN-BN. We will assess [C]raclopride BPND in ventral and dorsal putamen, ventral and DC and consider the influences of age, weight, and other relevant variables. These hypotheses will be tested by an unpaired t-test, with diagnosis as factor and [C]raclopride BPND as dependent variable. We will use Troendle's (1995) method to adjust for multiple comparisons. Based on our pilot data we expect to see [C]raclopride BPND of roughly 2.120 (CW), 2.404 (REC AN), 2.299 (REC BN), and 2.147 (REC AN-BN) in the AVS, with SDs of roughly 0.359 in each group. With 25 subjects per group, a (Welch-Satterthwaite) t-test will have power in excess of 90% to detect differences in [C]raclopride BPND between each of the ED groups and CW at the 0.05 level (two-sided). We will also regress log [C]raclopride BPND on group (REC AN, REC AN-BN, and REC BN, with CW as the reference group), controlling for age, height, and weight. To the extent that these additional covariates are associated with log [C]raclopride BPND, this will reduce the standard error associated with each of the group effects leading to improved power.

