**6. SPECIFIC AIMS**

How are individuals with restricting-type AN able to starve themselves and become emaciated while most people have difficulty losing a few pounds? Furthermore, why do individuals with BN tend to periodically overeat? Considerable data support our overarching hypothesis: Serotonin (5-HT) and dopamine (DA) functional activity, through actions on reward and inhibitory neural pathways, contribute to disturbed appetitive behaviors and extremes of self-control in AN and BN. In order to avoid the confounding effects of malnutrition and weight loss (and because our data suggest that recovered (REC) individuals have persistent trait-related alterations of DA and 5-HT function, we will study, over the course of 5 years, 25 REC AN, 25 REC AN-BN, 25 REC BN, and 25 age and body mass index (BMI) matched healthy control women (CW) who are 18 to 45 years old. We will use PET imaging with specific radioligands for the DA D2/D3 receptors (C]raclopride) and 5-HTT (C]DASB).

It is well known that 5-HT functional activity inhibits feeding. Considerable data suggest that AN and BN have different disturbances of 5-HT neural circuitry, which contributes to both restricted eating and overeating. **In AIM 1**, our data support the prediction that REC AN will have elevated, and REC BN will have diminished 5-HTT binding [e.g., [C]DASB binding potential (BPNondisplaceable tissue uptake (ND))] in midbrain and striatal regions) contributing to inhibition of appetite and other rewards in AN, and decreased self-regulatory control in BN. We predict REC AN-BN will have 5-HTT binding values that fall in-between REC AN and REC BN.

DA circuits play a key role in optimal response to stimuli. Our data support the possibility that AN and BN may have similar dysregulation of anterior ventral striatum (AVS) system function, making them vulnerable to dysfunctional modulation of the rewarding aspects of appetitive behaviors (and modulation of emotionality).

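### Aim 1 names and powers no comparison that locates REC AN-BN on the proposed continuum, and a non-significant t-test against CW would be weak support for no difference

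*Combined protocol and SAP*

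**What the plan says.** Section 9, Power and Statistical Analysis Plan, Aim 1, sets the objective as determining "whether there is a continuum of 5-HTT binding associated with diagnosis". Three predictions follow: binding is raised in REC AN, lowered in REC BN, and in REC AN-BN lies "between those of REC AN and REC BN and will probably not differ from CW. These hypotheses will be tested by an unpaired t-test". The in-between prediction also stands in Section 6, Specific Aims: "We predict REC AN-BN will have 5-HTT binding values that fall in-between REC AN and REC BN".

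On multiplicity the plan says "We will use Troendle's (1995) method to adjust for multiple comparisons". It does not list the comparisons in that family.

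Power is stated as follows: "With 25 subjects per group", "a (Welch-Satterthwaite) t-test will have power in excess of 80% to see a difference between the REC AN and CW". The same is said of REC BN versus CW. For REC AN-BN there is only an expectation, that its binding will lie between the other two eating-disorder groups "and (essentially) the same as CW".

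For Aim 1 the plan has no named contrast of REC AN-BN with REC AN or REC BN, no criterion for declaring a continuum, no equivalence margin and no confidence-interval rule.

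**The concern.** Two different kinds of hypothesis are assigned to an ordinary difference test.

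- **Ordering.** A continuum is a statement about where the middle group lies. Comparing REC AN with CW and REC BN with CW uses no REC AN-BN data, so those results are the same whether REC AN-BN is in the middle, equal to one neighbour or outside the range.
- **No difference.** A t-test of REC AN-BN against CW can agree with this prediction only through a non-significant result. With 25 per group, that result is common even when the true difference is sizeable.

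At stake is the part of Aim 1 that goes beyond two patient-versus-control differences. The study could observe the predicted pattern of p-values and report a continuum although nothing in the prespecified analysis had placed REC AN-BN.

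**Working it through.** **Inputs, all from Section 9, Aim 1.** Pilot means with the older ligand: CW 1.169, REC AN 1.316, REC BN 1.027, REC AN-BN 1.168. Scaling to DASB: 2.17. Within-group SD: 0.382. Group size: 25. Level: 0.05 two-sided.

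**1. Predicted DASB differences (pilot difference × 2.17).**
- REC AN − CW: 2.17 × 0.147 = 0.319
- CW − REC BN: 2.17 × 0.142 = 0.308
- REC AN − REC AN-BN: 2.17 × 0.148 = 0.321
- REC AN-BN − REC BN: 2.17 × 0.141 = 0.306
- REC AN-BN − CW: 2.17 × (−0.001) = −0.002

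The first two match the plan.

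**2. The plan's own power.** Standard error = 0.382 × √(2/25) = 0.108. The noncentrality is 0.319/0.108 = 2.95 and 0.308/0.108 = 2.85. With the noncentral t on 48 df, power is 82.5% for REC AN versus CW and 79.8% for REC BN versus CW. The normal approximation gives 84.0% and 81.3%. The stated power therefore reproduces to within rounding.

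**3. Precision for REC AN-BN minus CW.** Half-width of the 95% interval = t(0.975, 48) × 0.108 = 2.011 × 0.108 = 0.217. This is 0.217/0.319 = 68% of the predicted REC AN effect and 0.217/0.308 = 71% of the predicted REC BN effect.

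**4. Chance that a real REC AN-BN versus CW difference is non-significant (noncentral t, 48 df).**

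| True difference | Non-significant |
|---|---|
| 0.15 | 73% |
| 0.16 (half the REC AN effect) | 69% |
| 0.20 | 56% |

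**5. How well the planned p-values discriminate.** The predicted pattern is REC AN above CW, REC BN below CW, and REC AN-BN versus CW non-significant. By simulation, before any multiplicity adjustment, it appears in about 61% of trials when the planned means are true. It still appears in about 47% when REC AN-BN is truly 0.15 above CW, and in about 36% when it is 0.20 above.

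**6. Power to show the order.** Require REC AN > REC AN-BN and REC AN-BN > REC BN, each at two-sided 0.05 in the predicted direction. The separate powers are 83.0% (0.321) and 79.2% (0.306). Their product is 0.830 × 0.792 = 0.657. The two differences share the REC AN-BN mean with opposite sign (correlation −0.5), which lowers the joint power to about 63% by simulation. About 32 to 33 completers per group would give 80%. With each test one-sided at 0.05, joint power at 25 per group is about 78%.

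**7. Why a trend test does not do this job.** Simulated Jonckheere–Terpstra test across the three patient groups, one-sided 0.025, 25 per group, REC AN versus REC BN gap 2.17 × 0.289 = 0.627. It rejects in over 99.8% of runs when REC AN-BN is in the middle, but also when it equals REC AN, equals REC BN, or lies 0.15 outside either end. Requiring both adjacent contrasts rejects in about 2.5% of runs when REC AN-BN equals a neighbour, and in about 0.1% or fewer when it lies 0.15 outside.

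**8. Prospects for a sameness claim.** The plan gives no margin, so these are assumed. The probability that the 95% interval lies wholly inside ± the margin, under the planned means with 25 per group, is:

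| Assumed margin | Probability |
|---|---|
| 0.20 | 2% |
| 0.25 | 25% |
| 0.308 (REC BN effect) | 60% |
| 0.319 (REC AN effect) | 65% |

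**The case against.** The strongest reply is that the plan is under-specified here, not wrong. Three parts of it stand.

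- A reader might infer that t-tests cannot show ordering at all. That goes too far. Two significant directional t-tests on adjacent groups would show it, and because the plan does not list its pairs, it does not exclude them.
- A reader might infer that the investigators will report a non-significant result as sameness with CW. No such rule is written. The relevant phrases are hedged expectations, and Section 6 makes no sameness prediction for this group.
- A reader might infer that the main Aim 1 conclusion rests on a non-significant p-value. It does not. The leading predictions are REC AN raised and REC BN lowered, and difference tests against CW suit both.

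It is also fair to say that the documents never claim to establish equivalence and offer no basis for a margin.

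This does not dispose of the point. The plan expressly includes the REC AN-BN predictions among the hypotheses that the t-test will test. The comparisons that could show the order are neither named nor powered, and the named test has no route to the no-difference prediction other than non-significance.

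**Conclusion.** The concern holds in this limited form: Aim 1 commits to testing REC AN-BN's position with a difference test, powers only comparisons that leave that position open, and sets no criterion for the continuum or for sameness with CW. The stated power of more than 80% does not extend to the continuum; joint power for the order is about 63%. Non-significance against CW is weak evidence, with an interval half-width of 0.217 and a 56% chance of missing a true difference of 0.20.

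These figures assume normal data, a common SD of 0.382 (given in the plan as an upper figure), the 2.17 scaling, 25 completers per group and no multiplicity adjustment. A smaller SD would improve them; an adjustment could only lower power. The tests of REC AN and REC BN against CW remain valid as planned.

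**What to change.** In Section 9, Aim 1:

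1. Name two contrasts, REC AN > REC AN-BN and REC AN-BN > REC BN, and claim a continuum only if both are significant in the predicted direction (an intersection-union test). No splitting of alpha is needed within the pair.
2. State that this joint claim has about 63% power at two-sided 0.05 with 25 per group under the planned means. List which comparisons the Troendle adjustment covers and whether this claim is among them.
3. Do not substitute Jonckheere–Terpstra or another trend test, because the REC AN versus REC BN gap alone makes it reject.
4. Report REC AN-BN minus CW as an estimate with its 95% confidence interval. Do not conclude sameness from non-significance. Claim it only if the interval lies inside a margin that is justified and fixed before analysis; otherwise call the result inconclusive. If no margin can be justified, the estimate and interval are enough.

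The cost is plan wording and two contrasts on data already to be collected. The downside is that the continuum claim carries a lower stated power, and sameness with CW will probably be inconclusive.

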## **8. PROGRESS REPORT**

To date a total of 47 participants have been enrolled into the study. We have successfully completed a total of 46 [C]DASB (in 18 CW, 11 REC AN, 10 REC AN-BN, 7 REC BN) and a total 47 [C]raclopride scans (in 19 CW, 11 REC AN, 10 REC AN-BN, 7 REC BN).

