## 10. HUMAN SUBJECTS

Subject Population: We seek to recruit 30 REC AN, 30 REC AN-BN, 30 REC BN, and 30 CW, between ages 18 to 45 for the PET imaging studies. It is our experience from previous studies that it will be necessary to enroll an additional 20% of subjects due to drug failure, non-completion of PET studies, etc. Thus, we expect to complete PET studies in a total of 100 subjects (25 REC AN, 25 REC AN-BN, 25 REC BN, and 25 CW).

Only right-handed subjects will be included as screened by the Edinburgh Handedness Inventory. The rationale for including only female subjects is that AN, AN-BN and BN among males is relatively rare (less than 10% in our experience). Furthermore, because some males with AN, AN-BN or BN have many atypical features, they should be subjects of a different study. All subjects will be matched by age, IQ, income, race/ethnicity, and will be non-smokers. REC AN, REC AN-BN, REC BN, and CW will be matched by BMI. Subjects will be recruited locally and nationally to reflect the racial/ethnic composition of the United States, which encompasses a wide range of ethnically diverse individuals (i.e., 65.6% White persons, not Hispanic, 15.4% Hispanic or Latino origin, 0.2% Native Hawaiian and Other Pacific Islander, 4.5% Asian persons, 1.0% American Indian and Alaska Native persons, 12.8% Black persons, 79.8% White persons (<http://quickfacts.census.gov/qfd/states/00000.html>)). While every effort will be made to recruit participants in respective proportion to these demographics, it has been our experience that patients with AN, AN-BN and BN tend to be predominantly white. Subjects fulfilling all the inclusion, but none of the exclusion criteria, will be admitted to the study. No exclusion criteria shall be based on race or ethnicity.

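### Aim 1 names no covariate-adjusted model for its [11C]DASB group contrasts, unlike Aims 2A and 2B, so it may forgo precision and leaves any imperfect matching uncorrected

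*Combined protocol and SAP*

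**What the plan says.** In section 9, Power and Statistical Analysis Plan, Aim 1 predicts higher DASB BPND in REC AN and lower in REC BN than in control women (CW), with REC AN-BN in between. The test is stated in one sentence: "These hypotheses will be tested by an unpaired t-test with diagnosis as factor". Troendle's method handles multiplicity. No covariate, adjusted model or sensitivity model is named. Power is given as "With 25 subjects per group, a (Welch-Satterthwaite) t-test will have power in excess of 80" per cent, for REC AN vs CW "based on a mean difference of 0.319 and a within-group SD of 0.382" and for REC BN vs CW "based on a mean difference of 0.308 and a within-group SD of 0.382".

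Aim 2A, in the same section, tests its hypotheses by the same unpaired t-test. It then adds a regression of log raclopride BPND on group, age, height and weight. To the extent that these covariates are associated with the outcome, the plan says, "this will reduce the standard error associated with each of the group effects leading to improved power". Aim 2B describes its regression as controlling for the same three variables, although the model equation printed there does not contain them.

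On design, section 10 says: "All subjects will be matched by age, IQ, income, race/ethnicity, and will be non-smokers". It adds that all four groups will be matched on BMI. Section 6 also describes the controls as matched on age and BMI. Neither section says how the matching is done.

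**The concern.** The groups are formed by diagnosis, so a difference in DASB binding can reflect diagnosis or anything else that differs between the women. Age and body size are the variables the investigators chose to match on, and age, height and weight are those they chose to adjust for in the dopamine aims. The plan gives no reason for leaving them out of Aim 1, its only group comparison of 5-HTT binding.

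Two things could be lost:

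- **Precision.** If the covariates predict binding and matching works, their variance stays in the error term of an unpaired test, and the standard error is larger than it need be.
- **Comparability.** If matching is imperfect, the t-test carries what remains into the estimated group difference. Matching on BMI also does not match height and weight separately.

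**Working it through.** **Inputs, all from the Aim 1 text:** 25 women per group; differences 0.319 (REC AN vs CW) and 0.308 (REC BN vs CW); within-group SD 0.382, given as an upper limit; two-sided 0.05 per contrast.

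**Step 1. The differences.** Pilot means on the older ligand are scaled by 2.17:

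- REC AN vs CW: 2.17 × (1.316 − 1.169) = 0.319
- REC BN vs CW: 2.17 × (1.169 − 1.027) = 0.308

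Both agree with the plan.

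**Step 2. The plan's power, unadjusted.** The noncentrality is δ / (SD × √(2/n)), where √(2/25) = 0.2828. With equal n and SD, the Welch test has 2n − 2 = 48 df.

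- REC AN vs CW: 0.319 / (0.382 × 0.2828) = 2.95; power 82.5% (84.0% by the normal approximation)
- REC BN vs CW: 0.308 / (0.382 × 0.2828) = 2.85; power 79.8% (81.3% by the normal approximation)

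The stated figure is reproduced to within rounding. By the exact t, the second contrast is 0.2 points under 80% when the SD is at its ceiling.

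**Step 3. Power with age, height and weight in the model.** Let R² be the share of within-group DASB variance that the three covariates explain. The documents do not give it, so it is an assumption, shown over a range. The residual SD is 0.382 × √(1 − R²), and 48 − 3 = 45 df remain.

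| Assumed R² | Residual SD | REC AN vs CW | REC BN vs CW |
|---|---|---|---|
| unadjusted t-test | 0.382 | 82.5% | 79.8% |
| 0 | 0.382 | 82.4% | 79.7% |
| 0.05 | 0.372 | 84.2% | 81.6% |
| 0.10 | 0.362 | 86.1% | 83.7% |
| 0.20 | 0.342 | 89.8% | 87.7% |

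If the covariates explain nothing, adjustment costs about 0.1 point. Using all four groups in one model with a common variance leaves 100 − 4 − 3 = 93 df. Power at R² = 0 is then 83.2% / 80.5%, no lower than the t-tests. The table assumes that the covariate means are balanced between groups.

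**Step 4. What the plan reports for another outcome.** In Aim 2B (20 per group, difference 0.031), the plan says that controlling for these variables lowers the error SD from 0.048 to 0.034. Power by the same formula rises from 51.2% to 80.2%, matching the plan's 51% and its claim of over 0.80. The implied R² is 1 − (0.034/0.048)² = 0.50. That concerns change in raclopride binding and is not an estimate for DASB.

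All these figures are per contrast, before Troendle's adjustment.

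**The case against.** The strongest reply is that the design already deals with this. Groups are matched on age and BMI, and also on IQ, income and race/ethnicity. Weight is held to 90–120% of average body weight in every group, and scans fall in the early follicular phase. This stands in part: large imbalance is unlikely if matching works. It does not justify the unpaired test, which uses neither the matching nor the covariates.

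Second, the gain is conditional. The plan itself ties it to the strength of association, and none is given for DASB. This stands in full, which is why the result is a range starting slightly below zero. The halving of variance in Aim 2B cannot be carried over to another tracer and outcome.

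Third, Aim 2A's named test is the same t-test, with the regression as an addition. This stands too. What Aim 1 lacks is the adjusted model that Aim 2A places beside its t-test. A reader might infer that the regression should also become Aim 2A's lead test, but nothing shown here supports that.

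Fourth, a reader might take the Progress Report's DASB counts ("in 18 CW, 11 REC AN, 10 REC AN-BN, 7 REC BN") as evidence of poor matching, because most controls were scanned before most REC BN women. Recruitment order does not show imbalance: the remaining women in any group can still be chosen to match, and the documents give no age or BMI data by group.

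**Conclusion.** The point holds as a gap in Aim 1. It names only unadjusted t-tests for non-randomised groups, while the neighbouring aims use age, height and weight. Adding an adjusted model changes power by between −0.1 points (R² = 0) and about +7 to +8 points (R² = 0.20): 82.5% to 89.8% for REC AN vs CW and 79.8% to 87.7% for REC BN vs CW. These figures rest on the plan's differences, on an SD that the plan gives as a ceiling, and on an assumed R².

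Two stronger readings are not supported. One is that the Aim 1 contrasts are biased by age or body size. Any size put on that bias would need a covariate–DASB correlation and a group gap, and the documents give neither. The other is that the stated Aim 1 power is wrong for the test it names. It reproduces, and the 0.2-point shortfall for REC BN vs CW disappears at an SD of 0.380 (80.2%).

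**What to change.** In the Aim 1 analysis text:

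- Pre-specify a linear regression of DASB BPND on group, with CW as reference, controlling for age, height and weight.
- State the outcome scale. Aim 2A's regression is on log BPND, whereas the Aim 1 power inputs are on the raw scale.
- Apply Troendle's method to the group coefficients and state the resampling scheme, since resampling for covariate-adjusted coefficients has to be defined.
- Report the unadjusted t-tests alongside.

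The cost is three degrees of freedom and a few sentences in the SAP. The covariates are already used in Aims 2A and 2B, so no new data are needed.

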## Neuroimage Analysis

MRI-Based Region of Interest (ROI) Definition for analysis of PET Data. PET and MRI image sets are aligned using PET/MRI fusion software (IDL, ITT Visual Information Solutions). ROIs are defined on MRI images across all MRI slices passing through those structures using an ROI drawing tool (imagetool) by trained tracers (blind to the diagnosis) with established reliability. For the [C]raclopride and [C]DASB studies ROIs will include the three functional sub-divisions (limbic, associative and motor) of the striatum as outlined by Martinez *et al.*. The limbic striatum comprises the AVS; the associative striatum comprises the pre-commissural DC, precommissural dorsal putamen and postcommissural DC; the motor striatum comprises the post commissural dorsal putamen. For the [C]DASB studies, as outlined by Frankle *et al.*, The subcortical regions include thalamus, insula, midbrain, medial temporal lobe (a spatially weighted average of 5 limbic structures, the uncus, amygdala, entorhinal cortex, parahippocampal gyrus, and hippocampus). The neocortical ROIs are as follows: DLPFC, medial PFC, OFC, ACC, temporal and occipital cortex. The cerebellum will be used as reference region for both studies. A different set of ROIs are routinely utilized for fMRI studies. As a result, we will define a second ROI set that will be applied to the PET BPND maps and enable us to perform the integrative analyses to relate the PET and fMRI data in exploratory AIM 4.

Anatomically constrained functional regions of interest for fMRI analyses. One of our co-investigators, [name], in collaboration with his colleagues, has developed methods for reconstructing the cortical sheet based upon routine 3D T1-weighted MRI volumes. FreeSurfer not only allows for the accurate measurement of cortical thickness, it also provides a method for parcellation of the cortical surface, where each location on the surface is assigned a neuroanatomical label based upon probabilistic information estimated from a manually labeled training set. The ROIs that will also be used for fMRI analysis include: bilateral caudate, ventral striatum, medial PFC, ACC, DLPFC, medial OFC, inferior frontal gyrus, inferior parietal cortex, and AI.

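### Aim 1's power rests on scaling the pilot group differences by 2.17 but the SD by only 1.10; even so, REC BN versus CW falls marginally short of the claimed 80%

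*Combined protocol and SAP*

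**What the plan says.** All planning figures are in section 9, Power and Statistical Analysis Plan, Aim 1.

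- The preliminary study used the older tracer McN5652. Its mean binding potentials were "1.169 (CW), 1.316 (AN), 1.027 (BN), and 1.168 (AN-BN) in the dorsal raphe", "with a SD of 0.348 or less in each group".
- From further pilot data that are not shown, DASB values are expected to be "roughly 2.17-times higher than" those of McN5652 "in the midbrain, with only a" "slight increase in within-group SDs (less than 0.382 for" DASB).
- Power is then claimed to exceed 80% for REC AN vs CW (difference 0.319) and REC BN vs CW (difference 0.308), both with SD 0.382, using a Welch-Satterthwaite t-test with 25 per group at two-sided 0.05.

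The hypotheses concern the midbrain and the striatum. Under Neuroimage Analysis, the DASB regions comprise the striatal subdivisions and a further list: "The subcortical regions include thalamus, insula, midbrain, medial temporal lobe", and several neocortical areas. The dorsal raphe is not listed separately. The Progress Report records 46 completed DASB scans ("in 18 CW, 11 REC AN, 10 REC AN-BN, 7 REC BN").

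**The concern.** The two parts of the standardised effect are treated differently. The group difference is multiplied by 2.17 and the SD by about 1.10, so the effect size nearly doubles between the preliminary study and the power statement. An SD that grows more slowly than the mean is possible with a better tracer. But the plan reports no group difference measured with DASB, and it does not explain why the difference should grow in full proportion while the spread between women hardly grows.

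The power claim depends on this step and has almost no slack at the planning SD. If the DASB SD is moderately larger than 0.382, Aim 1 has clearly less power than stated, and a non-significant transporter result would carry less information than the plan suggests.

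**Working it through.** **Inputs (all from the Aim 1 power statement).** McN5652 means: CW 1.169, AN 1.316, BN 1.027. SD bound 0.348. Tracer ratio 2.17. DASB SD bound 0.382. n = 25 per group, two-sided 0.05 with no multiplicity adjustment. Section 11 plans 30 entered for 25 completed, so 25 is the analysed number.

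**Step 1: where the differences come from.**
- AN: 1.316 − 1.169 = 0.147; 0.147 × 2.17 = 0.319.
- BN: 1.169 − 1.027 = 0.142; 0.142 × 2.17 = 0.308.

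Both planning differences are therefore the dorsal raphe differences times the tracer ratio.

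**Step 2: scaling of the SD.** 0.382 / 0.348 = 1.10. Full proportional scaling would give 0.348 × 2.17 = 0.755.

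**Step 3: standardised effects.**
- AN: 0.147 / 0.348 = 0.42 before; 0.319 / 0.382 = 0.84 after.
- BN: 0.142 / 0.348 = 0.41 before; 0.308 / 0.382 = 0.81 after.

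The increase is 2.17 / 1.098 = 1.98-fold. The implied CW coefficient of variation falls from 0.348 / 1.169 = 30% to 0.382 / (2.17 × 1.169) = 15%.

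**Step 4: the plan's own figure.** With equal group sizes and SDs, the Welch test is close to the pooled t-test with 2 × 25 − 2 = 48 degrees of freedom and noncentrality (difference / SD) × √(25/2).
- AN: 0.835 × 3.536 = 2.95, power 82.5%.
- BN: 0.806 × 3.536 = 2.85, power 79.8%.

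A normal approximation gives 84.0% and 81.3%. The stated power is thus reproduced, except that for BN the t-test named in the plan falls just below 80%.

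**Step 5: sensitivity to the DASB SD.** Differences are held at 0.319 and 0.308.

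| DASB SD | Power, AN vs CW | Power, BN vs CW |
|---|---|---|
| 0.382 | 82.5% | 79.8% |
| 0.45 | 69% | 66% |
| 0.50 | 60% | 57% |
| 0.60 | 45% | 43% |
| 0.755 (scales fully with the mean) | 31% | 29% |

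The largest SD that keeps 80% power is 0.394 for AN and 0.381 for BN.

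**Step 6: detectable difference.** From Step 5, the standardised difference detectable with 80% power is 0.319 / 0.394 = 0.81. In DASB units that is about 0.309 at SD 0.382, 0.364 at 0.45, 0.404 at 0.50 and 0.611 at 0.755.

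**Step 7: what the existing scans can supply.** 18 + 11 + 10 + 7 = 46 scans in four groups give 46 − 4 = 42 degrees of freedom for a pooled within-group SD. Its 95% limits are about −18% and +27%. An estimate of 0.382 would carry limits of roughly 0.31 to 0.49, which exclude 0.755 but cannot separate 0.382 from 0.394.

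**The case against.** The strongest reply is that 0.382 is an empirical input. The plan attributes both the ratio and the small rise in SD to pilot data, and nothing in the documents contradicts them. A newer tracer with less noise relative to signal would raise the standardised effect, so slower growth of the SD is not in itself a defect. Both SDs are also bounds: 0.348 is a ceiling over four groups and 0.382 is an upper limit, so the true DASB SD could be smaller and power higher. All of this stands. It does not supply a DASB group difference, and it does not justify carrying the older difference over in full.

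Four stronger readings are tempting, and the documents do not support them.

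- **That true power is about 30%.** This needs an SD of 0.755, about twice the stated bound. It is the limiting case of proportional scaling and not a result shown anywhere.
- **That about 74% of the older tracer's variance must have been measurement noise**, from 1 − (0.382 / (2.17 × 0.348))². This treats two upper bounds as point estimates and assumes that every woman's value is multiplied by the same constant, whereas the plan gives only a rough overall ratio.
- **That the trial powers a contrast it will not test**, because the differences come from the dorsal raphe and the ratio from the midbrain. The dorsal raphe lies within the midbrain, and AN vs CW and BN vs CW in the midbrain are stated hypotheses. The mismatch is secondary and drives none of the figures above.
- **That the plan contains an arithmetic slip.** The multiplications are right, and the power follows from the inputs to within rounding and choice of approximation.

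It can also be said that the existing scans, used without group means, cannot confirm the assumed difference. That is true, which is why the detectable difference should be reported as well.

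**Conclusion.** The point holds as an unsupported planning assumption plus a marginal shortfall. Scaling the difference by 2.17 and the SD bound by 1.10 nearly doubles the standardised effect, and the power claim depends on it. At the plan's own inputs and named test, power is 82.5% for REC AN and 79.8% for REC BN, so the latter should read about 80%. Modestly larger SDs reduce power to 69%/66% (0.45) or 60%/57% (0.50), with 31%/29% as the limiting case.

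These figures assume normal data, equal SDs, 25 analysed per group and group differences exactly as planned. They use unadjusted 0.05, as the plan does, although it also specifies Troendle's adjustment. As a rough conservative bound, a level of 0.025 at the stated inputs would give about 74% and 70%. Which SD applies cannot be settled from the documents. The striatum, the other hypothesised region, has no power figure at all.

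**What to change.** In the Aim 1 paragraph of the Power and Statistical Analysis Plan:

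1. Restate power as a range over the DASB SD, as in the table, and correct the REC BN figure to about 80%.
2. State that carrying the preliminary group difference over at 2.17 is an assumption, and describe the pilot data behind the ratio and the SD.
3. Replace 0.382 with the pooled within-group SD for each tested region (midbrain and striatum), computed from the 46 DASB scans already acquired. Do this without comparing or reporting group means, and give the SD's confidence limits.
4. For each of those regions, report the group difference detectable with 80% power at 25 per group (about 0.81 times the SD, before multiplicity adjustment).

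The cost is one recalculation and revised wording. The sample size does not change and no extra participants are needed. The downside is that the stated power may fall.
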